Hypertensive individuals display a broader range of plasma renin levels than do nonhypertensive individuals (77). Laragh (78) found that hypertensives with low renin levels (about 20% of essential hypertensives) responded especially well to "volume" treatment, i.e., diuretics, while those with high renin levels responded to beta-blockers, which reduce renin levels. These findings formed the basis for the volume-vasoconstrictor theory of hypertension pathophysiology (78). Of particular relevance to DASH2, low renin levels are reportedly more

common in African Americans and older persons, also populations with greater salt sensitivity. Thus, the renin status of DASH2 participants may be a confounder for the blood pressure response to salt intake. In addition, Resnick et al. (79) reported that low renin individuals have a greater antihypertensive response to calcium supplementation, suggesting that the response to the DASH combination diet itself may be affected by renin status. Based on these considerations, we will categorize renin status in DASH2 by measuring plasma renin activity at the end of the 50 mmol sodium diet period. We have chosen this level of sodium because renin levels will be maximally stimulated, providing the clearest definition of low renin participants (80,81).

Biological Storage Samples

Numerous endogenous vasoactive substances and candidate genes related to blood pressure or cardiovascular risk may influence blood pressure response to the DASH combination diet and to sodium reduction. To facilitate future investigation of biological variables (e.g., plasma renin and angiotensin) and candidate genes (e.g., angiotensinogen), we will store plasma, serum, and 24-hour urine specimens taken at baseline (screening) and at the end of each feeding period, and buffy coat specimens taken once during intervention.

4. Study Design

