SV3 must occur at least seven days after SV2. The visit includes: blood pressure measurement; weight; a follow-up review of questions from the eligibility questionnaire (if needed); a review of DASH2 menus and specific food items; a review of the food frequency questionnaire; processing of the 24-hour urine specimen, which is analyzed centrally for Na, K, Ca, phosphorus, urea nitrogen, and creatinine; a fasting blood draw that is analyzed centrally for lipids; and completion of physical activity and GI symptom questionnaires. The 24-hour urine and fasting blood specimens are also processed for long-term storage for future analyses. The blood is separated into serum, plasma, and buffy coat.

Laboratory results from the SV2 blood draw should be reviewed prior to SV3 in order to determine if additional blood work (either fasting or nonfasting) is needed. It is not necessary to collect repeat eligibility bloods at SV3; such blood draws may occur either before or after SV3. Participants may not begin run-in feeding, however, until they have met all laboratory eligibility requirements.

SV3 blood pressure eligibility is based on the average of the six blood pressure measurements taken at SV1, SV2, and SV3. Table 3 lists the blood pressure eligibility cutpoints for SV3.

7. Run-In and Randomization

Run-In

All participants who are eligible based on the three screening visits undergo a run-in period on the control diet (at the higher sodium level) prior to randomization. The higher sodium level was chosen because it is most reflective of current intake and because, if a participant is going to reach a blood pressure escape level during the study, it is most likely to occur at this level of sodium intake.

The run-in phase has two main objectives: 1) to identify and exclude individuals who will not comply with the eating requirements of the trial; and 2) to determine the appropriate caloric level for each participant that is needed to maintain weight. Initial caloric requirements for the start of run-in feeding are calculated using the WHO equation (83) to estimate resting energy expenditure and an activity factor, derived from the Stanford 7-day physical activity questionnaire(84), previously used in DASH, that is used to obtain an estimate of total energy requirements.

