In addition to the exclusion criteria applied during the screening visits, participants may be excluded prior to randomization for unusually large weight swings or for noncompliance with the protocol. All participants whose weight changes by five percent or more between SV3 and the first day of run-in are excluded from the trial at that point. The average of the SV3 weight and the weights measured on the first two full days of run-in feeding the participant's *target* weight and is used as the reference against which to assess weight change during run-in feeding. The overall caloric content of the participant's meals is adjusted as needed in order to assure that the participant's weight remains stable.

Participants may also be excluded prior to randomization for missed meals, poor clinic attendance, and over- or under-consumption of food. Finally, clinical centers subjectively evaluate each participant's overall compliance and attitude just prior to randomization and may exclude participants on the basis of this assessment as well. A more detailed discussion of compliance assessment is provided in section 11 (Dietary Compliance).

Participants who exhibit non-compliant behavior during run-in feeding, but after randomization, are retained in the study. However, randomized participants who drop out of the study before starting any of the intervention feeding intervals are replaced provided that they have no knowl-edge concerning their randomization assignment.

Randomization

Randomization occurs during the second week and prior to the end of run-in feeding. The timing of randomization may vary from cohort to cohort, provided that it occurs at least nine days after the start of run-in feeding and at least three working days prior to the start of intervention feeding. The former criterion permits adequate assessment of dietary compliance, while the latter assures that the kitchen staff have adequate time to assemble and prepare the foods that are needed for the start of intervention feeding (they need to know each participant's dietary assignment). Within a feeding cohort at any given site, however, all participants are randomized at the same time.

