During each intervention feeding period participants receive all of their food from the clinic and eat at least one on-site meal per day, five days per week. As with the run-in feeding, the on-site meal should, if possible, be lunch or dinner.

Weight is recorded at each clinic visit during the intervention feeding periods. Blood pressure is assessed weekly during the first three weeks of each intervention feeding period. Five blood pressure measurements are recorded during the final nine days of each intervention feeding period, and at least two of these must occur during the final four days of feeding. All blood pressure assessments consist of a set of two random zero measurements. A 24-hour ABPM reading is also recorded during the final nine days of each intervention feeding period. Additional intervention measurements taken during the last nine days of intervention feeding include: a 24-hour urine (for analysis of Na, K, Ca, phosphorus, urea nitrogen, and creatinine for group analyses) and a fasting blood collection for measurement of lipid levels. Fasting blood samples are also obtained for renin determination, but only the samples obtained during the lower sodium level feeding period are actually analyzed. (The other samples are collected to preserve blinding among clinic staff.) Samples of urine, serum, and plasma, will be frozen and stored for future analysis. Medication use and symptom monitoring, an anonymous compliance survey, and a brief assessment of physical activity occur during the final seven days of each intervention feeding period.

All randomized participants complete an evaluation at the end of the third intervention feeding period summarizing their overall experience with the trial.

The average of all weight measurements recorded during run-in feeding plus the weight taken at SV3 defines the participant's *baseline* weight and is used as the baseline against which to measure weight change during intervention feeding. The overall caloric content of each participant's meals is adjusted as needed in order to assure that weight remains stable during intervention feeding.

Participants may discontinue feeding during a given feeding period provided that all of their measurements are complete and that the resulting break does not exceed the limits set above (i.e., two days following run-in and five days otherwise).

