DASH2 participants also provide a 24-hour ABPM reading during the last nine days of each intervention feeding period. The DASH2 ABPM measurement protocol is adapted from that advocated by the British Hypertension Society and is identical to that used in DASH. Staff obtain both the usual RZ measurements and ABPM readings when the monitor is placed in order to confirm satisfactory readings in the clinic setting. Participants are then asked to wear the device for a full 24-hour period. Upon return to the clinic, the data are downloaded to the computer and checked to confirm that at least 14 acceptable readings were obtained between the hours of 6 a.m. and 12 midnight. If so, the monitoring is deemed acceptable. If fewer than 14 acceptable readings are available during this timespan, the participant is asked to repeat the monitoring.

We will use 24-hour SBP as a secondary outcome analogous to RZ-DBP. Other ambulatory pressure indices, including 24-hour DBP and waking and sleeping pressures, will be used for exploratory analyses. "Waking" and "sleeping" pressures are calculated according to the times of going-to-sleep and awakening indicated by the participants on the day they wear the ambulatory monitor.

Other Outcomes

A standard lipid panel is run on (8-hour) fasting blood samples collected at SV3 and during the last week of each intervention feeding period. Total cholesterol, VLDL-C, HDL-C and triglyceride levels are measured directly, and LDL-C levels are calculated. These data are used to validate differences in dietary consumption between the control and combination diets and also to assess the impact of lower levels of sodium on total and LDL-C cholesterol. All analyses are done centrally, and a minimum fast of eight hours is required for the measurement to be valid.

Plasma renin activity is measured in samples drawn after an overnight fast and at least 90 minutes in the upright position. Samples are collected during the last week of each intervention feeding period, but only the samples corresponding to the lower sodium level diet are analyzed. A minimum fast of eight hours is required for this measurement. Renin level is measured to determine the extent to which renin profile influences blood pressure response to the DASH combination diet and sodium reduction.

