For all four aims, further secondary analyses will adjust for the potentially confounding effects of race, sex, age, body mass index, education, physical activity, and alcohol intake. Interaction terms are used to determine if any observed treatment effects differ for various subgroups. Additional analyses will test whether baseline renin status influences treatment differences.

Handling of missing data.

Participants not completing the post-randomization follow-up (either due to nonattendance at data collection visits or to protocol escape levels) are likely to represent a nonrandom subset of the overall randomized population. For example, those individuals who are required to initiate antihypertensive medications are likely to be the participants who would have had the highest end-of-intervention blood pressure levels. End-of-intervention blood pressure values for such participants are discussed in section 12 (Outcomes Measures).

Because of the cross-over nature of the study design, some dropouts will not have any BP measurements for one or more sodium levels. As described in section 12, we use the average of these individuals' screening blood pressures as their end-of-intervention blood pressures. The rationale for this rule is that, in essence, these individuals are just very noncompliant with the study diets, and our best estimate of their blood pressure on their usual diets is the average of their screening blood pressures. The only exception to this rule is for those individuals who are randomized but who never start any of the intervention feeding periods. Since loss to follow-up in these individuals cannot be related to treatment assignment, they are treated as if they were never randomized and excluded from all analyses.

Finally, subject to the preceding considerations, analyses are conducted using an intention-totreat philosophy, whereby each randomized participant is included in each analysis according to his/her randomly assigned diet group.

15. Sample Size / Statistical Power

The proposed sample size of 400 participants (200 in each of the combination and control diet arms) was selected to provide adequate power, both overall and within subgroups, for addressing specific aims #1 and #2. This section summarizes power computations to address all four of its specific aims. We assume two-sided alternative hypotheses for each specific aim, and we also include allowance for multiple testing adjustment, as indicated above.

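### Section 14 tests a baseline renin status that is never measured: the only renin assay comes after randomization, at the end of the lower-sodium period, so a diet-by-renin comparison is not protected by randomization

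*Protocol*

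**What the plan says.** The closing paragraph on the four aims in section 14 (just before the handling of missing data) lists further secondary work and ends: "Additional analyses will test whether baseline renin status influences treatment differences". The phrase is not limited to sodium, and Other Objective 3 in section 2 asks about the response to both the combination diet and sodium reduction.

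Three other places say when renin is measured:

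- Section 3, Plasma Renin: "we will categorize renin status in DASH2 by measuring plasma renin activity at the end of the 50 mmol sodium diet period". The reason follows: "We have chosen this level of sodium because renin levels will be maximally stimulated".
- Section 8, Procedures: samples are drawn in every period to keep clinic staff blinded, but "only the samples obtained during the lower sodium level feeding period are actually analyzed".
- Section 12, Other Outcomes: "only the samples corresponding to the lower sodium level diet are analyzed".

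On timing of assignment, section 7 says: "Randomization occurs during the second week and prior to the end of run-in feeding". At the last screening visit (section 6, SV3) the protocol plans "a fasting blood draw that is analyzed centrally for lipids". The rest of that specimen is stored, and section 3 names renin only as an example of possible future work on stored samples.

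**The concern.** The analysis section names a modifier that the measurement plan does not supply. Read literally, the test cannot be done. Read as intended, a value obtained during the intervention would be reported under a baseline label.

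The label matters because a baseline modifier and a post-randomization one support different conclusions. Classes formed from a baseline value split each diet arm in the same way, so the diet comparison within a class remains a randomized one. Classes formed from a value taken while participants eat the assigned diet need not do so. If the combination pattern moves renin, the people classed as low renin in one arm differ from those so classed in the other, and the difference in their blood pressure mixes the diet effect with that selection. A reader of the results would have no warning of this.

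**Working it through.** The protocol gives no figure for this analysis, so there is none to reproduce. The check is a comparison of passages, followed by an illustration whose inputs are mostly assumed.

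**1. Order of events**

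- Randomization: run-in week 2 (section 7), before any intervention feeding.
- Renin sampling: last nine days of a 30-day period (section 8) or its last week (section 12). If lower sodium comes first, the sample follows at least 30 − 9 = 21 days, or 30 − 7 = 23 days, on the assigned pattern.
- Lower sodium can fall in period 1, 2 or 3, since all six orders occur equally often (section 16, Data Management System). For two thirds of participants, one or two other sodium periods come first. The latest sample falls at the end of 3 × 30 = 90 feeding days.
- The blood pressures that define the lower-sodium outcome are taken in the same final nine days (section 8).

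Every assayed value is therefore post-randomization, and none is a baseline value.

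**2. What can affect the value**

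Section 3 says that the sodium level stimulates renin. It follows that a participant who does not eat the lower-sodium diet may be less stimulated. An effect of the dietary pattern itself is plausible, given the planned mineral contrast between the diets (2.5-fold, section 9), but the protocol neither states nor quantifies one. The accurate wording is that renin can be affected by diet and adherence.

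**3. Which contrasts are exposed**

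- Diet contrast and diet-by-sodium interaction: different people are compared across arms within a class formed after assignment. These are exposed.
- Sodium contrasts within a diet: each person is compared with himself or herself and keeps one class throughout. These are less exposed. Adherence can still link class and response.

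**4. Illustration**

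From the documents: between-person variance 150, within-person variance 40/5 = 8 (section 15), diet effect 5.5 mm Hg (section 3, the earlier DASH trial). Assumed: sodium effect 4 mm Hg, correlation of renin with blood pressure −0.3, renin measurement noise 0.5 SD, classes by median split, and no true modification by renin.

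If the combination diet raises renin by *s* SD, the within-class diet effect at lower sodium shrinks by approximately

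*s* × 1/(1 + 0.5²) × 0.3 × √150 × 2/π = *s* × 0.8 × 0.3 × 12.25 × 0.637 = 1.87*s*

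(2/π is the rate at which the mean of the lower half of a normal distribution moves with its cut-off.)

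| Assumed shift | Approximate within-class diet effect | Simulated (low, high renin), full adherence |
|---|---|---|
| 0 | −5.5 | −5.49, −5.53 |
| 0.25 SD | −5.5 + 0.47 = −5.03 | −5.03, −5.05 |
| 0.5 SD | −5.5 + 0.94 = −4.56 | −4.51, −4.58 |

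A split on a true baseline renin stayed close to −5.5 in all cases. For the sodium contrast with no diet shift, full adherence gave −4.00 and −3.99. With adherence varying between people (SD 0.3, capped at full), low and high classes gave −3.44 and −3.60, a false difference of 0.16 mm Hg. Section 15 puts the detectable sodium effect in half the sample at 1.1 to 1.4 mm Hg.

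These figures show the mechanism only. With no diet shift there is no distortion of the diet contrast, and the opposite sign for the shift or the correlation would reverse its direction.

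**The case against.** The timing is deliberate. Section 3 chose the lower level because it gives the clearest separation of low-renin participants, and measuring everyone at one sodium level standardizes the value. Section 2 keeps renin out of its list of baseline characteristics (Other Objective 1) and gives it a separate objective that speaks of a renin profile, as section 12 also does. The word baseline in section 14 thus looks like a single drafting slip. The analysis is additional, and section 14 says that analyses beyond the primary one serve interpretation and not decision.

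Much of this stands. The timing needs no defence for the sodium question, and the primary analysis is not at issue. But the slip sits in the section that governs analysis, and the objective it serves includes the diet response. A common sodium level removes differences in assigned sodium, not differences in assigned dietary pattern.

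A reader might infer something stronger: that non-adherent participants, being unstimulated, would fill the low-renin class and hide or reverse a true relation between low renin and salt sensitivity. The documents do not support this. They give no non-adherence rate, and poor compliers are screened out before randomization. They give no low-renin cut-off, and under a quantile cut the class would not grow. The 20% low-renin figure in section 3 refers to essential hypertensives, while hypertensives are planned as about 30% of this sample.

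**Conclusion.** The point holds as an inconsistency with a consequence for one secondary question. Section 14 names a baseline modifier, and the measurement plan provides only a post-randomization one. A diet-by-renin comparison within classes of that variable is not protected by randomization and cannot be reported as effect modification by a baseline characteristic. The sodium contrasts within each diet are less affected.

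The size of any bias is not derivable from the protocol. It depends on whether and how far the dietary pattern moves renin, on how renin relates to blood pressure, and on adherence, and none of these is given. It could be nil.

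A reader might also infer that the dietary pattern is known to drive the renin value. The protocol says this only of the sodium level. Aims 1 to 4, the sample size and the primary SBP analysis are unaffected.

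**What to change.** In section 14, replace baseline renin status with plasma renin activity at the end of the lower-sodium period. State that it will be examined as a modifier of the sodium contrasts within each diet. Add that any diet-by-renin result conditions on a post-randomization variable, is descriptive only, and is not evidence of modification by a baseline characteristic.

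This costs two or three sentences and no new data. The real price is that the diet half of Other Objective 3 then supports a weaker conclusion.

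An assay of stored SV3 plasma would give a true pre-randomization value, but it is at most an optional sensitivity analysis. It would reflect usual, uncontrolled sodium intake, and section 6 states no posture for that draw, whereas section 12 requires at least 90 minutes upright for the renin sample.
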